**Table 2: Analysis Visits for Regular Scheduled Visits (Continued)**

Visit	Target Day [Week]	Visit Window (Days)
Week 48	330 [48]	289 to 414 [41 to 60wk]
Week 72	498 [72]	415 to 582
Week 96	666 [96]	583 to 750
Week 120	834 [120]	751 to 918
Week 144	1002 [144]	919 to 1086

If there are 2 or more assessments in the same analysis visit, the closest one to the target day will be used in the analysis. If there are 2 assessments that are equally spaced from the target day, the latest one will be used in the analysis, unless otherwise specified.

**Table 3: Analysis Visits and Time-points for Additional Treatment Scheduled Visits**

Visit	Target Day* [Week]	Visit Window (Days)*
Extended treatment or retreatment		
Weekly Treatment Visits	$(w-1)7 + 1$ [w]	$(w-1)7 - 2$ to $(w-1)7 + 4$ , $w > 12$

\* Target day is relative to the first dose date in the extended treatment period.

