At site discretion, the 24-hour urine collection supplies for Weeks 24, 30, and 36 may be dispensed at this visit or at any point that is convenient to the patient and study site.

10.2.4. Extended Treatment Following Week 12

During the Extended Treatment Period, eligible patients will receive treatment with study drug according to the patient's originally assigned treatment group in a blinded fashion. Study drug treatment will be administered IV once weekly for 6 weeks. Extended Treatment Visit 1 should occur no later than 14 days from the date of T12.

Target dates for subsequent Extended Treatment Visits will be based on the Extended Treatment Visit 1 date. Extended Treatment Visits 2 through 6 must occur within \pm 3 days of the target date. A minimum of two calendar days must separate each administration of study drug.

If service is available in the region, if approval has been granted by the study site/institution as well as the relevant Ethics Committee or IRB, and if patient provides consent for the service, Extended Treatment Visits 3, 4, and 5 may occur at the patient's home with the support of a home nursing vendor selected by the sponsor.

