- Change from baseline in eGFR at 36 weeks in patients in the all-patients population (baseline 24-hour UPE  $> 1$  g/day) and in patients in the high-risk proteinuria group (baseline 24-hour UPE  $\geq 2$  g/day)
- Pharmacokinetics and pharmacodynamics of narsoplimab
- Occurrence of anti-drug antibodies (ADA) and, if present, neutralizing antibodies (Nab)

Exploratory endpoints are:

- Change from baseline in eGFR over time
- Change from baseline in 24-hour UPE over time
- Change from baseline in 24-hour uPCR over time
- Change from baseline in urine albumin/creatinine ratio (uACR) (from spot urine) over time
- Change from baseline in 24-hour uACR over time
- Achievement of  $\geq 50\%$  reduction from baseline in 24-hour UPE at any time post baseline
- Achievement of  $\geq 30\%$  reduction from baseline in 24-hour UPE at any time post baseline
- Duration of treatment response defined as the number of weeks between the first timepoint at which the patient achieves a  $\geq 30\%$  reduction from baseline in 24-hour UPE and the first timepoint at which the patient relapses (a relapse is defined as an increase in 24-hour UPE by  $\geq 30\%$  from the value of the lowest measured post-treatment UPE in a patient whose 24-hour UPE is  $> 1$  g/day)
- Achievement of 24-hour UPE of  $< 0.3$  g/day at 36 weeks (complete proteinuria remission)
- Duration of complete proteinuria remission defined as the number of consecutive weeks with UPE  $< 0.3$  g/day from the first timepoint at which UPE  $< 0.3$  g/day to the first timepoint at which UPE  $\geq 0.3$  g/day

- Duration of partial proteinuria remission defined as the number of consecutive weeks with UPE < 0.6 g/day from the first timepoint at which UPE < 0.6 g/day to the first timepoint at which UPE  $\geq$  0.6 g/day
- 24-hour UPE following retreatment in patients who relapse after treatment
- Change from baseline in the number of red blood cells per high-powered field (RBC/HPF) over time from baseline
- Change from baseline in biomarkers of complement activity and disease pathology in kidneys, serum, plasma, or urine. Biomarkers may include, but not necessarily be limited to:
  - Mannan-binding lectin (MBL) (serum and urine)
  - Complement component 4a (C4a) (urine)
  - C4d (urine)
  - Kidney injury molecule 1 (urine)
  - Neutrophil gelatinase-associated lipocalin (urine)
  - Clusterin (urine)
  - Markers of tubular and glomerular damage
  - Soluble membrane attack complex (urine)
  - Collectin-11 (urine)

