## 2.7. Analysis Visits

Two sets of analysis visits will be used. The first set ([Table 2](#)) is derived from the regular scheduled visits regardless of additional treatments (extended treatment, relapse retreatment, re-initiation of treatment open-label treatment, and open-label relapse retreatment; see the schedule of events in the protocol). Longitudinal data analyses will be based on the regular scheduled visits and time will be calculated from Day 1, unless otherwise specified.

The second set is derived for the additional treatment scheduled visits ([Table 3](#)).

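### SAP Table 3 counts additional-treatment visits from the first extended dose but only for w > 12, so extended visits get no analysis window and the footnote contradicts the week range

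*SAP*

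**What the plan says.** SAP Section 2.7 defines two sets of analysis visits. Table 2 covers the regular visits, counts from study Day 1, and serves the longitudinal analyses. For the rest, "The second set is derived for the additional treatment scheduled visits", which is Table 3. Section 2.7 lists extended treatment, relapse retreatment, re-initiated treatment and open-label treatment as additional treatments.

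Table 3 has one row, "Extended treatment or retreatment". The target day for week w is (w−1)×7 + 1 and the window runs from (w−1)×7 − 2 to (w−1)×7 + 4, for w > 12 only. The footnote fixes the origin: "Target day is relative to the first dose date in the extended treatment period".

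Protocol Section 10.2.4 describes the extended course: "Study drug treatment will be administered IV once weekly for 6 weeks", and "Target dates for subsequent Extended Treatment Visits will be based on the Extended Treatment Visit 1 date". On its start: "Extended Treatment Visit 1 should occur no later than 14 days from the date of T12". Only patients whose UPE exceeds 1 g at Week 12 receive it (Protocol Section 7.1). Relapse retreatment is a later course of 6 weekly doses (after Week 24, 30 or 36) or 12 weekly doses (after Week 48 or 72), under Protocol Section 10.2.7.

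**The concern.** A count that starts at the first extended dose cannot begin at week 13 and still cover a six-week course. Retreatment shares the same origin, so the first dose of a retreatment course is labelled by time elapsed since an earlier, different course. Patients who never had the extended course have no origin at all.

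At stake are the descriptive tables by scheduled visit in SAP Sections 3.4.2 to 3.4.4 (laboratory, vital signs, ECG), so far as they show additional-treatment visits. Also at stake is any by-visit display of the exploratory endpoint "24-hour UPE following retreatment in patients who relapse after treatment" (SAP Section 2.1). A programmer would have to supply a rule that the plan does not state, possibly after the study-level unblinding at the interim analysis (SAP Section 2.9.5).

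**Working it through.** **Inputs**
- Target, window and w > 12: SAP Table 3. Origin ExT1: its footnote.
- Extended course: 6 weekly visits dated from ExT1, ExT2 to ExT6 within ±3 days (Protocol Sections 10.2.4 and 20.2.2).
- T12 target: study Day 78 (SAP Table 2). ExT1: at most 14 days after T12.
- First retreatment dose: within 7 days of receiving the central laboratory result (Protocol Sections 10.2.7.1 and 10.2.7.2). Laboratory turnaround is not stated.

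**Step 1: check the formula against Table 2.** (w−1)×7 + 1 for w = 12, 24, 30, 36, 48, 72, 96 gives 78, 162, 204, 246, 330, 498, 666. All equal Table 2. So Table 3 uses the study-week formula that Table 2 applies from Day 1.

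**Step 2: first window in Table 3.** For w = 13 the target is 12×7 + 1 = 85 and the window is 82 to 88, counted from ExT1.

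**Step 3: extended visits.** Planned days are 1, 8, 15, 22, 29 and 36. The latest in-window day is 36 + 3 = 39. If two missed visits are made up after a COVID-19 interruption, it is 36 + 14 + 3 = 53. None reaches Day 82, so 0 of 6 have a window. The exception is a patient whose extended course is interrupted for three or more visits and who restarts at T1 (Protocol Section 20.4.3). A second extended course could then fall after Day 82 of the original ExT1.

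**Step 4: retreatment counted from ExT1.** Relative day = UPE target day + lag − ExT1 day + 1. Assumptions: ExT1 on study Day 85 or 92 (7 or 14 days after the T12 target), and first retreatment dose 7 or 14 days after the UPE target day.

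| Relapse at | UPE target day | Relative day, ExT1 Day 85 | Relative day, ExT1 Day 92 | Label of first dose |
|---|---|---|---|---|
| Week 24 | 162 | 85, 92 | 78, 85 | none, or w 13–14 |
| Week 30 | 204 | 127, 134 | 120, 127 | w 18–20 |
| Week 36 | 246 | 169, 176 | 162, 169 | w 24–26 |
| Week 48 | 330 | 253, 260 | 246, 253 | w 36–38 |
| Week 72 | 498 | 421, 428 | 414, 421 | w 60–62 |

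Example: 162 + 7 − 92 + 1 = 78, which lies before Day 82 and so has no label. With ExT1 anywhere on Days 83 to 94, the full urine-collection windows and a lag of 1 to 14 days, the ranges widen to none or 13–15, 16–21, 22–28, 33–41 and 57–65.

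**Step 5: other origins, keeping w > 12.**
- Each course's own first dose: the last visit of a 12-week course is at latest Day 78 + 3 = 81, one day before the first window. Nothing is captured.
- Study Day 1: ExT1 on Day 85 gives weeks 13 to 18 for ExT1 to ExT6, and ExT1 on Day 92 gives weeks 14 to 19. An ExT1 before Day 82 (for example Day 79) would have no label.

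**Step 6: coverage.** Patients with Week 12 UPE of 1 g or less have no ExT1 date, so any later retreatment visit has no origin. The 12-week open-label and 6-week open-label extended courses (Protocol Section 10.2.8) have no row.

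**The case against.** The best defence is that this is a footnote slip. The formula is Table 2's, and w > 12 from study Day 1 begins at Day 85, about when extended treatment starts. Read that way, the table gives nearly every extended and retreatment visit a window, and every patient has an origin. This stands as the likely intent, but it contradicts the footnote, still shifts labels by a week with the start date, and leaves open-label visits without a row.

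It can also be said that no analysis section cites Table 3, that the protocol's visit names identify each sample, and that extended-period dates still fall in Table 2's wide windows (Initial Treatment Visit 12, Days 5 to 120; Week 24, Days 121 to 183). This limits the harm. But the SAP does not say that protocol visit names replace Table 3, and the closest-to-target rule would usually select another value within those Table 2 windows.

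Two stronger readings are tempting. A reader might infer that a body of extended-treatment laboratory data disappears. The schedule in Protocol Section 20.2.2 does not support that: it has no metabolic panel or blood count, only weekly vital signs, ECG at ExT1, urinalysis at ExT1 and ExT4, spot urine ratios at ExT4 and one 24-hour urine. A reader might also infer that a dose-by-dose UPE response to retreatment is lost. Only one 24-hour UPE is scheduled per course, at 6RT6 or 12RT12 (Protocol Sections 20.2.4 and 20.2.5), so there is no such profile to lose.

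**Conclusion.** The point holds as a rule that fails as written. With the stated origin, 0 of 6 extended visits have a window, apart from the COVID-19 restart case. Some Week 24 retreatment starts also have none, and other retreatment visits carry labels that vary with each patient's dates. Patients without an extended course have no origin, and open-label courses have no row. The extended-visit result needs only the documents' own figures. The worked retreatment labels rest on the assumed ExT1 days and lags.

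The effect is small and descriptive: mainly vital signs, with some ECG, urine and retreatment laboratory data, and any by-visit display of UPE after retreatment. A reader might infer a threat to the confirmatory results. There is none: the primary UPE analysis takes its visits from Table 2 (SAP Section 2.9.2), and the eGFR slope analysis uses actual assessment day from randomization (SAP Section 2.9.2.3). Type I error and sample size are untouched. It should be corrected because the contradiction is plain and the repair is cheap.

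**What to change.** Replace Table 3 with one row per course, each counted from that course's own first dose:
- extended, w = 1 to 6
- 6-week retreatment, w = 1 to 6
- 12-week retreatment, w = 1 to 12
- open-label, w = 1 to 12
- open-label extended, w = 1 to 6

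Keep the window of 3 days either side of target, but open the w = 1 window at Day 1 (Days 1 to 4) so that it takes in no pre-course days. Remove w > 12. Each dose number then has the same label in every patient.

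At minimum, re-anchor the footnote to study Day 1, accept that labels then vary with the start date, and add open-label rows. Either version costs one SAP table and its derivation, needs no new data, and should be settled before the interim unblinding.

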## 2.8. Handling of Missing Data

The following general methods will be used for producing the data summaries and documenting missing data:

- Available clinical data at each visit will be presented and the sample size displayed will reflect the number of patients with available data. Patient listing data will be provided as recorded on the case report form, indicating partial dates and missing data
- Generally, if data are missing or incomplete, the missing or incomplete values will be presented in the data listings. Data summaries will be based on the observed data without imputation, unless otherwise specified
- If there are 2 or more assessments in the same analysis visit, the closest one to the target day will be used in the analysis. If there are 2 assessments that are equally spaced from the target day, the latest one will be used in the analysis, unless otherwise specified

Multiple imputation-based sensitivity analyses relating to primary and key secondary efficacy endpoint missing data are described in Section 2.9.2.2.

[figure not shown]
## 2.9. Statistical Assessment of the Study Objectives

### 2.9.1. Multiplicity Comparisons and Multiplicity

The primary UPE endpoint will be analyzed and formally tested for treatment comparison with first 180 patients in the high-risk proteinuria group through 36 weeks in the FAS population. The primary efficacy endpoint (change in log-transformed 24-hour UPE from baseline to 36 weeks in the high-risk proteinuria group) and the 2 key secondary endpoints will be tested sequentially to preserve the overall type I error rate of 5% as depicted in Figure 2.

## Key Secondary Efficacy Endpoints:

1. the rate of change in eGFR over 2 years in high-risk proteinuria group
2. the rate of change in eGFR over 2 years in the all-patients population

**Figure 2: Overall Type I Error Control for the Primary and Key Secondary Endpoints**

Abbreviations: UPE = urine protein excretion; +ve = P-value  $\leq 0.05$  in a 2-sided test; -ve = P-value  $> 0.05$  in a 2-sided test; g = grams; d = day.

If the primary efficacy endpoint is statistically significant at 5% level in a 2-sided test, then the key secondary endpoint (1), the rate of change in eGFR over 2 years in the high-risk proteinuria group (baseline UPE  $\geq 2$  g/day), will be tested in a two-sided test at 5% level of significance. If the key secondary eGFR endpoint for the high-risk proteinuria group is statistically significant in a two-sided test at 5% level, then the key secondary eGFR endpoint (2), the rate of change in eGFR over 2 years in the all-patients population (baseline UPE  $> 1$  g/day), will be tested in a two-sided test at 5% level.

Testing of other efficacy endpoints will not be subject to type-1 error control and, therefore, will be viewed as supportive.

### 2.9.2. Efficacy Analyses

Unless otherwise specified, time will be calculated from Day 1.

**Table 2** will be used to determine the analysis values and the timepoints to be used in the analysis regardless of missed visits, extended treatment, or re-initiation of treatment.

The UPE primary efficacy endpoint in the high-risk proteinuria group is unaffected by the associated blinded SSRE and, hence, no special considerations apply to the analysis of UPE data pre and post the planned SSRE.

### **2.9.2.1. Analysis of the Primary UPE Efficacy Endpoint in the High-Risk Proteinuria Group (Baseline UPE $\geq 2$ g/day)**

The primary efficacy endpoint will be based on the natural logarithm transformed 24-hour UPE. Descriptive statistics for the log-transformed 24-hour UPE change from baseline to 36 weeks, the geometric mean ratio (GMR) relative to the study baseline, and the coefficient of variation in percentage will be provided by treatment group for the FAS population.

The primary analysis will be a MMRM analysis on the change from baseline in log-transformed 24-hour UPE at Week 12, Week 24, Week 30, and Week 36. The model will be fitted in SAS via the PROC MIXED procedure. Terms will be included for treatment, time (as a categorical variable for the four timepoints), treatment by time interaction, and randomization strata as fixed effects. Within patient error will be modeled using an unstructured covariance matrix. Log baseline UPE will be included as a covariate in the model. Restricted maximum likelihood method will be used to estimate the model parameters. If the estimation of the model fails, an autoregressive (1) [AR(1)] covariance structure will be used. SAS code will be of the form,

```
PROC MIXED DATA=X METHOD=REML;
  CLASS PATIENT RANDTRT VISIT STRATA;
  MODEL CHG_BL = BASE RANDTRT VISIT RANDTRT*VISIT STRATA
    /DDFM=KR;
  REPEATED VISIT / PATIENT = PATIENT TYPE = UN;
  LSMEANS RANDTRT*VISIT/SLICE=VISIT PDIFF DIFF ALPHA=0.05 CL;
  ODS OUTPUT DIFFS=DIFF LSMEANS=LSMEANS;
RUN;
STRATA: Baseline eGFR level ( $\geq 30$  to  $\leq 45$  mL/min/1.73 m2 and  $> 45$  mL/min/1.73 m2)
```

The difference in least squares (LS) means at Week 36 between the treatment groups and its 95% confidence interval (CI) will be estimated. Two-sided p-value will be calculated. The LS mean at Week 36 will be estimated with 95% CI for each treatment group. The ratio of the GMR between the treatment groups will also be estimated with 95% CI.

### **2.9.2.2. Primary UPE Efficacy Endpoint Sensitivity Analyses**

Sensitivity of the primary efficacy endpoint relate to the handling of missing data.

#### **Jump to Placebo Multiple Imputation**

The first approach will employ a control-based multiple imputation [Ratitch 2011] whereby missing observations in both the narsoplimab and placebo groups are imputed using only data observed in the placebo group; as such, this approach reflects a 'jump to placebo (or reference)' analysis. Imputation of values in the placebo arm will assume missing at random (MAR) while imputation of values in the narsoplimab arm will assume missing not at random (MNAR), i.e. as if the patient had been a member of the placebo arm. This approach does not assume a sustained benefit of narsoplimab treatment after discontinuation and limits a post-discontinuation effect to that of placebo. The approach will be implemented as follows:

- Step 1: Non-monotone missing data will be imputed first based on the MAR assumption and a multivariate joint Gaussian imputation model using Markov chain Monte Carlo (MCMC) method as per the MCMC statement in the SAS® PROC MI procedure. As a result, each imputed dataset will only have missing data at the end of patients' records, (a monotone missing data pattern). The MCMC method in the MI procedure will be used with multiple chains (option CHAIN=MULTIPLE), 100 burn-in iterations, and a non-informative prior. A separate imputation model will be used for each treatment arm. The imputation models will include the randomization stratification factors, baseline log UPE and change in log UPE at each time point. In case of non-convergence or non-estimability issues, a ridge prior and a single model will be considered with treatment arm added as explanatory variable to the model.
- Step 2: The remaining, monotone, missing data will be imputed using sequential regression multiple imputation model estimated based on data from the *placebo arm only*. Each sequential regression model (i.e., for imputation of values at a given time point) will include the stratification factors, baseline log UPE, and all previous values of UPE. Missing values at a given time point in placebo and narsoplimab treatment arms will be imputed from the same imputation model, conditional on patient values observed or imputed at previous time points.
- Step 3: The log change from baseline in UPE to each scheduled post-baseline visit will be calculated, based on observed and imputed data. Each of the imputed complete datasets from Step 2 will be analysed with the same MMRM model used for the primary analysis.
- Step 4: The results of the analysis of each imputed dataset, i.e., treatment effect estimates and their standard errors, will be combined via the SAS® PROC MIANALYZE procedure using Rubin's rules [Rubin 1987] to produce an overall treatment effect estimate and its associated 95% confidence interval and 2-sided p-value.

Example SAS code of the form to perform this first sensitivity analysis is contained in [Appendix 1](#).

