## APPENDIX 1. JUMP TO PLACEBO MULTIPLE IMPUTATION

A control-based pattern-mixture model approach as per [Ratitch 2011] whereby missing observations in both the narsoplimab and placebo groups are imputed using only data observed in the placebo group; this model reflects a ‘jump to placebo (reference)’ analysis.

Several steps are required to execute this sensitivity analysis.

In the first step, intermittently missing data (e.g., where a patient has week 12 and week 36 data recorded but has week 24 data missing) are imputed as non-monotone missing to generate a monotone missing pattern. The form of the associated SAS code is given below where the dataset **DATAIN** has already been sorted by randomized treatment (**RANDTRT**) and the randomization stratification factors **STRAT1** and **STRAT2**:

```
/*FIRST STEP IMPUTE NON-MONOTONE (INTERMITTENTLY) MISSING DATA*/
PROC MI DATA=DATAIN SEED=<VALUE> NIMPUTE=20 OUT=MI_OUT1;
  VAR BASE W12 W24 W30 W36 ;
  MCMC CHAIN=MULTIPLE PRIOR=JEFFREYS IMPUTE=MONOTONE ;
  BY STRAT1 STRAT2 RANDTRT ;
RUN;
```

where **BASE** = baseline log UPE, and **W12**, **W24**, **W30** and **W36** = week 12, 24, 30 and 36 change from baseline log UPU values.

The resulting dataset **MI\_OUT1** is then sorted by **\_IMPUTATION\_**, **STRAT1**, **STRAT2** and **RANDTRT**. In the second step, **PROC MI** is called again utilizing the regression method under **MNAR** to complete imputation of the monotone missing datasets resulting from the first step. The SAS code will be of the following form:

```
/*SECONDLY IMPUTE MONOTONE MISSING DATA AS MNAR JUMP TO PLACEBO*/
PROC MI DATA=MI_OUT1 SEED = <SEED> NIMPUTE = 1 OUT=MI_OUT2;
  BY _IMPUTATION_ STRAT1 STRAT2 ;
  CLASS RANDTRT ;
  MONOTONE REG (W36 = BASE W12 W24 W30/ DETAILS) ;
  MNAR MODEL (W12 W24 W30 W36 / MODELOBS =(RANDTRT = 'PLACEBO')) ;
  VAR W12 W24 W30 W36 BASE ;
RUN;
```

The dataset **MI\_OUT2** contains the 20 complete imputed data sets. This dataset will be transformed in a third step such that, for each patient, each post-baseline time-point is represented by a separate record.

```
/*THIRD STEP TRANSFORM IMPUTED DATASETS*/
DATA MI_OUT3; SET MI_OUT2 ;
  VISIT=12; CHG_BL=W12-BASE; OUTPUT ;
  VISIT=24; CHG_BL=W24-BASE; OUTPUT ;
  VISIT=30; CHG_BL=W30-BASE; OUTPUT ;
  VISIT=36; CHG_BL=W36-BASE; OUTPUT ;
RUN;
```

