The 20 complete datasets in **MI\_OUT3** will then be analyzed in a fourth step by MMRM via **PROC MIXED** as specified for the primary endpoint. The SAS code will be of the following form:

```
/*FOURTH STEP MMRM ANALYSIS OF IMPUTED DATASETS*/
PROC MIXED DATA=MI_OUT3 METHOD=REML;
  BY _IMPUTATION_;
  CLASS PATIENT RANDTRT VISIT STRAT1 STRAT2;
  MODEL CHG_BL = BASE RANDTRT VISIT RANDTRT*VISIT STRAT1 STRAT2
    STRAT1*STRAT2 /DDFM=KR;
  REPEATED VISIT / PATIENT = PATIENT TYPE = UN;
  LSMEANS RANDTRT*VISIT/SLICE=VISIT PDIFF DIFF ALPHA=0.05 CL;
  ODS OUTPUT DIFFS=DIFF LSMEANS=LSMEANS;
RUN;
```

To obtain overall LSmean and treatment effect estimates, the **DIFF** and **LSMEANS** datasets are merged in a fifth step prior to combination across imputations using Rubin's rule in a sixth step via **PROC MIANALYZE**. The SAS code will be of the following form:

```
/*FIFTH STEP MERGE DIFF AND LSMEANS DATASETS*/
DATA DIFF2;
  SET DIFF (IN=A) LSMEANS;
  IF A THEN COMPARISON=RANDTRT||' VS '||LEFT(_RANDTRT);
  ELSE COMPARISON=RANDTRT;
RUN;
PROC SORT DATA=DIFF2;
  BY COMPARISON _IMPUTATION_;
RUN;

/*SIXTH STEP COMBINE MI ESTIMATES VIA MERGE DIFF AND LSMEANS
  DATASETS*/
PROC MIANALYZE DATA=DIFF2;
  BY COMPARISON;
  MODELEFFECTS ESTIMATE;
  STDERR STDERR;
  ODS OUTPUT PARAMETERESTIMATES=MIESTS;
RUN;
```

The output dataset **MIESTS** contains the final, imputed results. The resulting multiply imputed means and difference in means between narsoplimab and placebo will be presented, along with the associated SEs, CIs and 2-sided p-values.

The same approach will be used for the analysis of the two key secondary endpoints, with **BASE** = baseline eGFR and log UPE change from baseline values at **W12**, **W24**, **W30** and **W36** replaced by absolute eGFR values at weeks **W12**, **W24**, **W36**, **W48**, **W60**, **W72**, **W84** and **W96**.

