*%macro dat(nsim,n,acc,k,fup,xfup,vis,ve,vb,d);
%datx(1000,180,45,      2,9 ,24,3,42.3499,0.5411,1);
%datx(1000,280,56.125,2,24,24,3,42.3499,0.5411,2);

data max;
  set d2;
  maxvslope=vslope;
keep g nsims maxvslope;
run;

/*
proc print data = max;
title 'max xx';
run;
title;
*/
data all;
  set d1 d2;
run;

proc sort data = all;
by g nsims acc      fup      xfup      vis      ve      vb      n ;
run;

proc sort data = max;
by g nsims ;
run;

/*
proc print data = all;
title 'all check';
run;
title;
*/
data all;
  merge all max;
  by g nsims;
  vslope2arm = vslope*2;
  vmax = maxvslope*2;
  Fishi = 1/vslope2arm;
  FishF =1/vmax;
  inf= Fishi/FishF;
  if k=1 then kc='Uniform ['||left(trim(put(round(k,0.1),3.1)))||']      ';
  if k>1 then kc='Non-Uniform ['||left(trim(put(round(k,0.1),3.1)))||']';
run;

/*

```

```
proc print data = all;
title 'all max merged check';
run;
title;
*/
```

```
proc print data = all split='*' noobs;
where g=0;
var dat nsim kc acc fup xfup vis vb ve n Fishi FishF inf;
label dat='Run'
      nsim='##Sims'
      kc='Accrual*Type'
      acc='Accrual*Time* (months)'
      fup='Min FollowUp* (months)'
      xfup='Max FollowUp* (months)'
      vb = 'vb*monthly* (mL/min/m2) ^2'
      ve = 've*(mL/min/m2) ^2'
      n = 'Total*N'
      vis='Visit*Freq* (months)'
      fishi='Interim*Fishers Inf'
      fishf='Final*Fishers Inf'
      inf='Inf*Fraction';
run;
```

```
proc datasets lib=work
  nolist kill;
quit;
run;
```

```
proc printto log=log;
run;
```

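### The jump-to-placebo imputation is really copy-reference: it carries part of the earlier narsoplimab benefit forward, contrary to the stated property, and the Appendix 1 code also subtracts baseline twice from the UPE arm means

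*SAP*

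**What the plan says.** SAP 2.9.2.2 gives the control-based multiple imputation a name, "as such, this approach reflects a 'jump to placebo (or reference)' analysis", and a property: "This approach does not assume a sustained benefit of narsoplimab treatment after discontinuation and limits a post-discontinuation effect to that of placebo". Protocol 14.1.10.1 repeats the property but not the algorithm.

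The algorithm is in SAP 2.9.2.2, Step 2. Sequential regressions are estimated in placebo patients only, with strata, baseline log UPE and all earlier values as predictors. Missing values in both arms "will be imputed from the same imputation model, conditional on patient values observed or imputed at previous time points". Appendix 1 codes the same thing, "MONOTONE REG (W36 = BASE W12 W24 W30/ DETAILS", with placebo patients as the modelling set. Appendix 1 then extends it to eGFR: "The same approach will be used for the analysis of the two key secondary endpoints".

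Appendix 1 also defines W12 to W36 as "week 12, 24, 30 and 36 change from baseline log UPU values". Its third step nevertheless reads "VISIT=12; CHG_BL=W12-BASE; OUTPUT", and the same for the later visits. It says that the imputed arm means will be presented along with their difference.

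**The concern.** Jump-to-reference puts a narsoplimab patient with missing data on the placebo mean profile whatever was observed earlier. Copy-reference treats the patient as a placebo patient who happened to have those earlier values. If they were low because of narsoplimab, the prediction stays low, and part of the benefit survives in the imputed values. The SAP names the first method, states its property, and specifies the second.

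This analysis is pre-specified for the primary endpoint and both key secondary endpoints, and SAP 2.9.5 foresees that the UPE result may support regulatory filings. As it stands, the report would say that post-withdrawal benefit had been removed when only part of it had been.

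The second issue is a coding matter. If W is already a change, W − BASE removes baseline twice.

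**Working it through.** No printed figure in the documents quantifies this property, so there is none to reproduce first.

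**Carried share.** Let B = Cov(target, observed) · Var(observed)⁻¹ from the placebo covariance, and m the narsoplimab-minus-placebo mean shift at the observed times (0 at baseline). The imputed narsoplimab mean lies B·m away from placebo. True jump-to-reference gives 0.

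**UPE at Week 36.** From the SAP: a 35% effect, N = 180, SD 0.63 (blinded) or 0.80 (planning). I use ln 0.65 = −0.431; the printed −0.393 corresponds to 32.5%. Assumed, because the documents do not give them: the correlations, a constant effect over visits, and 15% missing at Week 36.

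- Equal correlation c between visits, after k observed visits: share = kc / (1 + (k − 1)c). For c = 0.5: 0.50, 0.67, 0.75.
- Conditioning on baseline as the mean of two collections, with one common raw correlation r: c = (r − q)/(1 − q), where q = r²/((1 + r)/2). For r = 0.5, q = 0.333 and c = 0.25, giving 0.25, 0.40, 0.50. For r = 0.8, q = 0.711 and c = 0.31, giving 0.31, 0.47, 0.57.
- AR(1) over the four visits, baseline ignored: share = ρ^(4 − k). For ρ = 0.5: 0.125, 0.25, 0.50.

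With 5% lost after each of visits 1, 2 and 3, the overall log effect is ln 0.65 × (0.85 + 0.05 × sum of shares). For AR(1) 0.5 that is −0.431 × (0.85 + 0.05 × 0.875) = −0.385. SE = 2·SD/√180, i.e. 0.0939 at SD 0.63 and 0.1193 at SD 0.80.

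| Method / assumed covariance | Share after 1/2/3 visits | Log effect | Reduction | z (SD 0.63) | z (SD 0.80) |
|---|---|---|---|---|---|
| True jump-to-reference | 0/0/0% | −0.366 | 30.7% | 3.90 | 3.07 |
| SAP, AR(1) 0.5 | 13/25/50% | −0.385 | 32.0% | 4.10 | 3.23 |
| SAP, baseline-conditioned r 0.5 | 25/40/50% | −0.391 | 32.4% | 4.16 | 3.28 |
| SAP, baseline-conditioned r 0.8 | 31/47/57% | −0.395 | 32.6% | 4.21 | 3.31 |
| SAP, compound symmetry 0.5 | 50/67/75% | −0.407 | 33.5% | 4.34 | 3.42 |
| SAP, AR(1) 0.8 | 51/64/80% | −0.408 | 33.5% | 4.35 | 3.42 |
| SAP, compound symmetry 0.8 | 80/89/92% | −0.422 | 34.5% | 4.50 | 3.54 |

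If a quarter of the dropouts have no post-baseline value (3.75% after each of 0 to 3 visits), the SAP method gives −0.380 to −0.408, or 31.6–33.5%. A simulation of Step 2 itself (placebo-only Bayesian regressions on baseline and earlier values, correlation 0.5 given baseline, dropout spread over the three later visits) retained 64–65% of the effect in imputed patients. The closed form gives (50 + 67 + 75)/3 = 64%.

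**eGFR at Month 24.** The residual variance 42.3499 and monthly slope variance 0.5411 are the SAP's high-risk values (Appendix 3: "datx(1000,280,56.125,2,24,24,3,42.3499,0.5411,2"). Times are 3-monthly from 0 to 24, with placebo covariance v + 0.5411·t·t′ + 42.3499·I and a mean shift proportional to t. The intercept SD is not given; I take 10 to 30. The all-patients components are 0.6539² and 5.9517² (SAP 1.3.2).

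| Last observation | High-risk group | All patients | True jump-to-reference |
|---|---|---|---|
| Month 3 | 11% | 11% | 0% |
| Month 9 | 49–50% | 48–49% | 0% |
| Month 12 | 65–67% | 64–66% | 0% |
| Month 18 | 85–86% | 85% | 0% |

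**Double subtraction.** BASE is a linear covariate in the MMRM, without a visit interaction. Replacing the response by response − BASE lowers its coefficient by exactly 1 and lowers each arm's LS mean by the mean log baseline. In the high-risk group that is at least ln 2 = 0.69, so each geometric mean ratio is divided by at least 2. In one simulated trial (geometric mean baseline 3.05 g/day, random-intercept mixed model standing in for the MMRM), the difference was −0.541 and its SE 0.116 both ways. The LS means moved from 0.066 and −0.476 to −1.048 and −1.589, so ratios of 1.07 and 0.62 would read 0.35 and 0.20.

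**The case against.** The algorithm is fully disclosed, and imputing as though the patient belonged to the placebo arm is a fair description of copy-reference. Nobody following the SAP would run a different analysis; one sentence and a label are wrong. Treatment is a fixed course of 12 weeks, or 18 with extension, so apart from relapse retreatment the Week 24 and Week 30 values are largely off drug by design. Carrying such an effect forward may be as reasonable as sending the patient to the placebo mean. That stands: the choice of method is a judgement, and relabelling is a sufficient repair.

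Step 2 conditions on baseline, which favours the lower part of the UPE range. This also stands in part. With one common raw correlation the excess is about 2 points. The compound-symmetry rows apply only if their correlation is read as what remains after baseline adjustment.

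Few values may need imputing, because Protocol 8.3.1 asks patients who stop drug to complete all visits. The tipping-point analysis is meant to reach full loss and reversal of effect. For eGFR, only the share carried into an imputed value is shown, not the effect on the slope difference or its p-value. The double subtraction sits in example code, and Step 3 of the text would be right if W were log UPE; checks might well catch it. These points limit the consequence. None makes the stated property true.

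**Conclusion.** Both parts hold.

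The method specified is copy-reference. It is still more conservative than missing-at-random for these patients, but less so than its label and stated property. The direction follows from positive within-patient correlation and a beneficial effect already seen; the size rests on assumptions. For UPE, at 15% missing and a true 35% effect, the estimate is about 1 to 4 points more favourable than under true jump-to-reference, and every case remains clearly significant. For eGFR the carried share is larger, about half or more once a patient has been followed to Month 9, using the SAP's variance components and an assumed intercept SD of 10 to 30.

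The primary test is unaffected. The double subtraction distorts only the displayed UPE arm means; the treatment difference, SE and p-value stand. It does not arise for eGFR, where Appendix 1 uses absolute values. This should be corrected, but it does not threaten the trial's main inference.

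**What to change.** Make the method and the stated property agree, in one of two ways:

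- Keep the algorithm, call it copy-reference, and delete the sentence on sustained benefit from SAP 2.9.2.2 and Protocol 14.1.10.1. This costs wording only.
- Keep the name and property, and impute narsoplimab patients from the placebo mean profile with their residuals taken around the narsoplimab mean. This needs standard reference-based imputation code and gives a somewhat less favourable sensitivity estimate.

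Apply the same choice to both eGFR endpoints.

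In Appendix 1, either define W12 to W36 as log UPE and keep the subtraction, or keep them as changes and set CHG_BL equal to W at each visit. Align the wording of Steps 1 and 3 in SAP 2.9.2.2. The cost is one definition or four short assignments.
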